#### **1. How soon after you wake do you smoke your first cigarette?**

|   |   |
|---|---|
|  Within 5 minutes |  31 to 60 minutes |
|  6 to 30 minutes  |  After 60 minutes |

## CONFIDENTIAL

**2. Do you find it difficult to refrain from smoking in places where it is forbidden? (e.g., in church, at the library, in the cinema)?**

- YES
- NO

**3. Which cigarette would you hate to give up?**

- The first in the morning
- Any other

**4. How many cigarettes per day do you smoke?**

- 10 or less
- 21 to 30
- 11 to 20
- 31 or more

**5. Do you smoke more frequently during the first hours after waking than during the rest of the day?**

- YES
- NO

**6. Do you smoke when you are so ill that you are in bed most of the day?**

- YES
- NO

### 8.4 Assessment of Level of Risk

This study presents minimal risk, as the interventions do not involve any invasive or risky medical procedures and can be considered no greater risk than ordinarily encountered in daily life. The potential benefit of study participation includes successful smoking cessation. Although documented risks of smoking cessation apps have rarely if ever been demonstrated, potential risks may be considered minimal and no greater than those associated with standard of care behavioral therapies for smoking cessation. In this context, the benefit-risk balance for study participation is considered highly favorable. Furthermore, this trial will ascertain potential adverse events via medical monitoring procedures and will be conducted in compliance with the protocol, good clinical practice (GCP), and the applicable regulatory requirements.

Both Clickotine and QuitGuide were developed to follow US Clinical Practice Guidelines for smoking cessation interventions. Use of either app may produce risks caused by the nicotine withdrawal associated with any attempt to quit smoking, including irritability and insomnia. Both QuitGuide and Clickotine are commercially available apps. Neither includes manufacturer's safety warnings nor involves any medical recommendations regarding use of prescription or over the counter quit aids.

## 9. DATA SAFETY AND MONITORING PLAN

This Data and Safety Monitoring Plan has been approved by NIDA for grant 1R43DA045395- 01 “Clinical trial of an innovative digital therapeutic for smoking cessation with biochemical verification.”

## **9.1      Oversight**

Medical monitoring of this study will be provided by [name]., Ph.D. The Study PI ([name]) will have the primary responsibility for data and safety/confidentiality monitoring during the trial.

## **9.2      Plan for Monitoring for Safety/Confidentiality**

The Study PI ([name]) will have the primary responsibility for monitoring the trial. [name] will meet monthly with the research coordinator to monitor data entry and completeness, as well as to ensure appropriate safety data monitoring and reporting. [name] will regularly monitor potential risks and procedures for protecting against risks and will monitor the progress of the study, including periodic assessments of data quality and timeliness, participant recruitment, accrual and retention, participant risk, and other factors that can affect study outcome. The PI will also consider factors external to the study, such as scientific or therapeutic developments that may have an impact on the safety of the participants or the ethics of the study.

Data and Safety Monitoring Board: National Institute of Drug Abuse (NIDA; funding this study) determined that a Data and Safety Monitoring Board (DSMB) was not necessary and will not be created for this trial.

Frequency of Data and Safety Monitoring: [name] will meet monthly with the research coordinator to monitor data entry and completeness, as well as to ensure appropriate safety data monitoring and reporting.

Monitoring of Safety Data: For the purpose of monitoring the safety of the study, the PI will review not only adverse events (AEs) and serious adverse events (SAEs), but other data that may reflect differences in safety between treatment groups. This includes treatment retention rates, reasons for drop-out, physical and emotional discomforts associated with being in the study, and side effects. In the event that differences between groups are apparent, the PI will consult with NIDA to determine further evaluation of safety.

Serious Adverse Events: Expedited review will occur for all events meeting the FDA definition of Serious Adverse Events (SAEs) – i.e., any fatal event, immediately life-threatening event,

permanently or substantially disabling event, event requiring or prolonging inpatient hospitalization, or any congenital anomaly. This also includes any event that a study investigator judges to impose a significant hazard, contraindication, side effect, or precaution. For purposes of this study, all SAEs will be required to be reported to the IRB and NIDA, regardless of any judgment of their relatedness to the study intervention. All relevant information will be reported including information about the event and its outcome, the subject's medical history and current conditions, and any relevant laboratory data. Information will be reviewed and a determination made of whether there was any possible relevance to the study intervention. Reporting to Western IRB and NIDA will be done within 72 hours of detection of the SAE.

Non-Serious Adverse Events: In monthly data review meetings, the PI will review summaries of the numbers and rates of adverse events by treatment group compiled by the research coordinator. These reports will include types of events, severity, and outcome if available. At the same intervals, the PI will also receive summary reports of treatment retention and reasons for drop-out, by treatment arm. In the event that differences in AE or retention rates between groups are apparent, the PI will consult with NIDA to determine further evaluation of safety.

Study Stopping Rules: If at any time during the course of the study, the PI or NIDA judges that risk to subjects outweighs the potential benefits, either shall have the discretion and responsibility to recommend that the study be terminated.

Monitoring of Data Quality: In the monthly Data and Safety monitoring meeting the PI will receive a report on data quality and completeness. At a minimum, this will include an overview of the progress of patient intake and retention; summary reports describing patient compliance with surveys and CO monitoring as described in the protocol; and a summary of the completeness and quality of key data elements needed to characterize patients and their primary and secondary outcomes.

Data and Safety Monitoring Reports: After the monthly meetings, the PI and research coordinator will prepare a summary report of their findings regarding safety and data quality based on data received to that point in the study. This report will include a brief description of the trial; baseline sample characteristics as available; summary of all safety findings; as well as an assessment of protocol compliance and data quality.

### **9.3 Adverse Events**

If an adverse event experienced by a participant, and the participant or their physician determines they should cease use of the study app, the participant will be withdrawn from the study.

Participants will have access to the e-mail and phone number of a study coordinator in case they experience any adverse event during the study.

## **CONFIDENTIAL**

If an adverse event is reported and evaluated by the study physician and is deemed to be severe enough to require withdrawal from the study, the participant will be withdrawn. Participants will have access to the e-mail and phone number of a study coordinator in case they are experiencing discomfort with Clickotine®.

All Adverse Events that occur during study participation will be solicited from study participants in both groups via an email-based system for reporting AE/SAEs. Participants are made aware of the email system during the informed consent and study enrollment process. Reports are reviewed by the research coordinator and the PI within 24 hours of the report and conveyed to the Medical Monitor (MM) for review and follow-up if appropriate. A Medical Monitoring form (See Appendix 12.6) is completed for each AE reported to the MM, to include: a description of the event; onset/offset dates; treatment required and/or condition resolution; designation as AE/SAE; and judgment of association with study intervention.

Expedited review will occur for all events reported by study participants that meet the FDA definition of Serious Adverse Events (SAEs) – i.e., any fatal event, immediately life- threatening event, permanently or substantially disabling event, event requiring or prolonging inpatient hospitalization, or any congenital anomaly. This also includes any event that a study investigator judges to impose a significant hazard, contraindication, side effect, or precaution. Reporting to NIH will be done according to NIH regulations governing SAE reporting: the PI will contact NIDA within 72 hours after the detection of a SAE. Reporting of Suspected Unexpected Serious Adverse Reactions (defined by WIRB as "unanticipated adverse device effects") to Western IRB will be done within 5 days of the report in accordance with WIRB policy.

## **10. STATISTICAL CONSIDERATIONS**

### **10.1 General Considerations**

All study analyses will be conducted after the study database is locked. All analyses will be performed on the intent-to-treat (ITT) population.

### **10.2 Analysis Populations**

#### Intent to Treat (ITT) population

All participants randomized to a study app that are able to confirm download of installed treatment arm app via telephone on the randomization date will be included in the ITT cohort.

### **10.3 Primary Endpoint**

The primary endpoint will be self-reported 30-day abstinence from smoking on the outcome survey as per Russell Standard Self- Reported 4-Week Quitter status.

30-day smoking cessation status (dichotomous variable: yes/no) will be compared between the CKT and QuitGuide groups utilizing logistic regression. Two-sided p-values will be calculated from logistic regression models, with adjustments to the models by: race, education, nicotine dependence, and living with a partner who smokes, consistent with previous studies' models.

#### **10.4 Secondary Endpoint**

Concordance rates between self-reported 30-day abstinence and the remote CO monitoring result will be estimated, with concordance > 85% considered evidence of a valid reporting process by Magellan Behavioral Health. Concordance rates will be compared between users that submit the CO measurement under video monitoring and those that do not. Upon completion of the Outcome Survey, participants will be invited to submit the CO assessment over a live video feed to confirm identity, until videos are received from 25 CKT users and 25 QG users. After 25 videos are received from each group, participants will no longer be invited to submit the CO assessment over live video feed.

Secondary analysis of the subgroup of NRT/pharmacotherapy users will be conducted to compare cessation rates between the CKT+NRT group and the CKT-only group, to confirm the initial trial result that CKT+NRT is not superior to CKT-alone.

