## **CONFIDENTIAL**

assessed; Concordance rates between users that submit the CO measurement under video monitoring and those that do not will be assessed. Hypotheses are that groups will not demonstrate significantly different concordance rates, demonstrating the validity of both the self-report and biochemical verification procedures.

As some users are expected to choose to begin using smoking cessation pharmacotherapy or NRT during their quit attempt, users will be permitted to begin using smoking cessation pharmacotherapy or NRT during the trial if they so choose. A secondary objective of the study is to compare cessation rates between the CKT+NRT group and the CKT-only group, to address expected med/NRT use during the trial and to confirm the initial trial result that CKT+NRT is not superior to CKT-alone.

A secondary objective of the study is to demonstrate the feasibility of evaluating CKT in a Magellan Behavioral Health (A Click Therapeutics partner) value-based care population. Half of the study sample will be recruited from a Magellan value-based care population.

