### **3. STUDY DESIGN**

#### **3.1 Overview of Study Design, Doses and Control Groups**

The overarching study aim is to recruit a population of current smokers who are motivated to quit with the assistance of a mobile solution, enroll them into a study testing apps to help them quit, and randomize them into one of two arms. The core study period will consist of 8 weeks of usage of Clickotine or QuitGuide. At the end of this period, users will receive notifications to link them to an online survey, which will record their responses in a secure database. The primary outcome is successful short-term quitting, measured by 30-day point prevalence abstinence (self-reported and confirmed with expired CO < 7ppm). This study includes rigorous methodological standards to address potential limitations inherent to digital and behavioral interventions. In implementing an effective active control in a hypothesis-blind manner, the study sets a particularly high bar for establishing superiority of CKT. However, the investigators find it essential to use this strong control in order to demonstrate clear evidence of effectiveness that will be understood as clinically meaningful by Magellan Health and other providers, payers, and regulatory agencies.

All subjects will be encouraged to submit a CO sample using an iCO Smokerlyzer device at Week 4 and Week 8 (study completion). The iCO Smokerlyzer device will be mailed to participants after study randomization. Week 4 CO assessment submission is a compliance check and only recorded as a data point of successful submission. The CO assessment will be conducted during the outcome assessment after the 8-week study period regardless of self-reported smoking status.

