## **6.2 iCO Smokerlyzer**

Participants will receive an iCO Smokerlyzer to be used at the user's discretion periodically throughout the trial regardless of treatment group. At Week 4 (Day 28), participants will be asked to submit an exhaled CO assessment to ensure the Smokerlyzer works properly, to identify any issues and as an adherence check. At the time of the Outcome Survey, participants will be required to submit another exhaled CO assessment, which will be recorded as a study endpoint.

Upon completion of the Outcome Survey, participants will be invited to submit the CO assessment over a live video feed to confirm identity, until videos are received from 25 CKT users and 25 QG users. After 25 videos are received from each treatment group, participants will no longer be invited to submit the CO assessment over live video feed and will instead receive a reminder to remotely submit an exhaled CO assessment.

In order to conduct the CO assessment via live video monitoring, participants must have access to another device with video capabilities, such as another mobile device or computer. Participants that are invited to conduct the CO assessment via live video monitoring will consent to participate in live video monitoring at the end of the outcome survey by answering "Yes" or "No". Study participants that answer "Yes" and will then be linked to schedule a video call via Calendly with the research coordinator. Participants will have the option to select their preference of video platform on Calendly.

During the live video monitoring participants will be required to provide a personal ID to confirm identity. Participants who consent to participate in the live video CO assessment will receive an additional \$50 Amazon gift card for their participation.

Those who do not consent to participate in the live video monitoring CO assessment will receive a reminder to submit the end of study CO assessment.

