### **8.3 Assessment of Efficacy**

To assess 30-Day Sustained Abstinence from Smoking (NACQ, 2016) participants are asked the following questions in the Outcome Survey to determine Russell Standard Self- Reported 4-Week Quitter status (West et al., 2005):

1. Have you smoked (even a puff) in the last 30 days?

- a. Yes
- b. No

2. (If yes, this question will appear) Have you smoked (even a puff) in the last 14 days?
  - a. Yes
  - b. No
3. (If yes, this question will appear) Have you smoked (even a puff) in the last 7 days?
  - a. Yes
  - b. No

The Outcome Survey will instruct subjects to submit an exhaled carbon monoxide (CO) reading with the iCO Smokerlyzer they were mailed after participant randomization. iCO Smokerlyzer devices will be programmed to email the exhaled carbon monoxide measurement results to the research coordinator directly.

The primary outcome, 30-day abstinence from smoking, will be assessed via self-report on the outcome survey. Confirmation with the remote CO assessment will be conducted to assess concordance between self-report and remote CO assessment results. Abstinence as per the CO assessment will be defined as an iCO reading of fewer than 7ppm exhaled CO.

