### **11. QUALITY CONTROL AND QUALITY ASSURANCE**

#### **11.1 Data Collection**

Data collection during the 8-week study will occur through the Baseline Survey, Smokerlyzer Confirmation (Day 28), the Outcome Survey at 8 weeks and the iCO Smokerlyzer assessment.

Primary outcome data, including covariates to be included in regression analyses, are acquired via the web-based baseline survey and outcome survey. Data are conveyed via an automated process from the web-based survey into a format matching the study database. Research coordinator is responsible for entering the survey data into the study database within 72 hours of survey completion.

Secondary outcome data: 1) CO readings are automatically conveyed via email by the iCO Smokerlyzer App to the study coordinator, who will enter the result into the database (a numerical value in parts-per-million (ppm; <7 ppm is defined as evidence of cigarette abstinence); 2) self-reported NRT and smoking cessation pharmacotherapy use (including e- cigarette use) will be acquired via the outcome survey.

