Primary outcome data, including covariates to be included in regression analyses, are acquired via the web-based baseline survey and outcome survey. Data are conveyed via an automated process from the web-based survey into a format matching the study database. Research coordinator is responsible for entering the survey data into the study database within 72 hours of survey completion.

Secondary outcome data: 1) CO readings are automatically conveyed via email by the iCO Smokerlyzer App to the study coordinator, who will enter the result into the database (a numerical value in parts-per-million (ppm; <8 ppm is defined as evidence of cigarette abstinence); 2) self-reported NRT and smoking cessation pharmacotherapy use (including e-cigarette use) will be acquired via the outcome survey.

Data Analysis Plan:

[name], will conduct all study analyses after the study database is locked. All analyses will be performed on the intent-to-treat (ITT) population, with non-response imputed as continued smoking. 30-day smoking cessation status (dichotomous variable: yes/no) will be compared between the CKT and QuitGuide groups utilizing logistic regression. Two-sided p-values will be calculated from logistic regression models, with adjustments to the models by: race, education, nicotine dependence, and living with a partner who smokes, consistent with previous studies' models.

Concordance rates between self-reported 30-day abstinence and the remote CO monitoring result will be estimated, with concordance > 85% considered evidence of a valid reporting process by Magellan Behavioral Health. Concordance rates between the video-monitored and unmonitored groups will be compared to determine the value of video monitoring the CO assessment.

Secondary analysis of the subgroup of NRT/pharmacotherapy users will be conducted to compare cessation rates between the CKT+NRT group and the CKT-only group, to confirm the initial trial result that CKT+NRT is not superior to CKT-alone.

Quality Assurance

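### Concordance objective: a null video comparison with no margin is taken as validation, the CO cut-off differs between the two documents, and the >85% benchmark has no stated denominator

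*Protocol*

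**What the plan says.** **Video comparison.** Protocol 2.2 compares concordance between participants who give the CO sample on live video and those who do not, and states: "Hypotheses are that groups will not demonstrate significantly different concordance rates, demonstrating the validity of both the self-report and biochemical verification procedures". Protocol 10.4 and SAP 10.4 say only that the rates will be compared. The Data Analysis Plan in the SAP file (within the Data and Safety Monitoring Plan) gives a different purpose, judging what video monitoring adds. None of them states a test, a margin or a power. Invitations stop once 25 videos per arm are in. Under Protocol 6.2 the video route needs consent, earns an extra $50, and "participants must have access to another device with video capabilities, such as another mobile device or computer".

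**CO cut-off.** Protocol 3.1 words the primary outcome as "measured by 30-day point prevalence abstinence (self-reported and confirmed with expired CO < 7ppm". Protocol 8.3 has: "Abstinence as per the CO assessment will be defined as an iCO reading of fewer than 7ppm exhaled CO". Protocol 11.1 has "<7 ppm is defined as evidence of cigarette abstinence". The Data Acquisition text of the monitoring plan in the SAP file has "<8 ppm is defined as evidence of cigarette abstinence".

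**Benchmark.** Protocol 10.4, SAP 10.4 and the Data Analysis Plan share one rule, under which exceeding the threshold shows that reporting can be trusted: "Concordance rates between self-reported 30-day abstinence and the remote CO monitoring result will be estimated, with concordance > 85% considered evidence". Protocol 3.1 has CO collected "regardless of self-reported smoking status".

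**Missing data.** Protocol 10.1 and SAP 10.1 put all analyses on the ITT population. Only the Data Analysis Plan adds that non-response counts as continued smoking. No passage exempts the concordance analysis.

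**The concern.** Failing to find a difference is not evidence that none exists, least of all in a small comparison where participants choose their own group. Under Protocol 2.2 an uninformative result would be reported as validating both self-report and remote CO testing.

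The 85% threshold is the only success criterion for this objective, and it depends on choices the documents leave open: who is in the denominator, which CO reading counts as abstinent, and what happens when a measure is missing. If these are settled after the data are seen, whoever settles them can decide whether the benchmark is met. The monitoring plan's summary also links this work to basing reimbursement on remote verification of abstinence, so the verdict will be used.

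**Working it through.** **The plan's own figure.** The stated sample size concerns the primary endpoint only: rates 0.262 and 0.083, two-sided α 0.05, power 85%, 78 per arm. The pooled normal formula is n = [1.96√(2p̄(1−p̄)) + 1.036√(p₁(1−p₁)+p₂(1−p₂))]² / (p₁−p₂)² with p̄ = 0.1725. It gives 78.4, so 79 per arm, and 84.8% power at 78. The stated figure reproduces. The concordance analyses have no counterpart.

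**Inputs.** ITT sample 156 (Protocol 4.1). Pilot retention 87.7% (Protocol 1.3), assumed to carry over with every completer submitting CO: 156 × 0.877 = 137 completers and 19 missing. Video group at most 25 + 25 = 50, leaving 137 − 50 = 87. Concordance levels are assumed; the documents give none.

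**Step 1: power of the video comparison.** Two-sided 5% score test, exact enumeration, 50 video users against 87 others:

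| Concordance, video / other | Power |
|---|---|
| 95% / 85% | 45% |
| 85% / 95% | 52% |
| 90% / 80% | 32% |
| 80% / 90% | 39% |
| 85% / 75% | 28% |
| 75% / 85% | 32% |

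For 20-point differences (85/65, 90/70 and 95/75, in either direction) power is 74-93%.

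**Step 2: precision.** Half-width of the 95% interval = 1.96√(p(1−p)(1/50 + 1/87)):
- p = 0.85: 12.4 points
- p = 0.90: 10.4 points

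Even an observed difference of exactly zero would leave differences of this size open.

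**Step 3: denominator.** Claimed 30-day abstainers at the planning rates: 78 × 0.262 + 78 × 0.083 = 20.4 + 6.5 = 26.9, about 27. The other completers number 137 − 27 = 110. Two illustrations, not predictions:

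| Assumed data | CO confirmation among claimed abstainers | Agreement among all with CO |
|---|---|---|
| 7 of 27 abstainers read high; all 110 others agree | 20/27 = 74.1% (fails) | 130/137 = 94.9% (passes) |
| All 27 confirmed; 21 of 110 self-reported smokers read low | 27/27 = 100% (passes) | 116/137 = 84.7% (fails) |

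**Step 4: missing data, conditional.** Suppose the non-response rule covers the CO result as well as the survey. The 19 people missing both measures then count as smokers on both, hence concordant. Among those measured, 114/137 = 83.2% fails; with the 19 added, 133/156 = 85.3% passes. The verdict flips only for 114 to 116 concordant of 137: 113 gives 132/156 = 84.6%, which still fails, and 117/137 = 85.4% passes unaided.

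**Step 5: cut-off.** A reading from 7 to below 8 ppm is abstinent under the monitoring plan and not under the Protocol. The effect on concordance cannot be computed without a CO distribution, which the documents do not give.

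**The case against.** The strongest reply is that this is an unpowered secondary aim in what the SAP file calls a brief feasibility study, and that most of the repair is editorial. That stands as to weight. Specific points:

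- **Where the inference sits.** A reader might infer that the whole analysis plan equates non-significance with validity. Only Protocol 2.2 does.
- **Benchmark undefined.** A reader might infer that concordance has no definition at all. That is too strong: both components and a cut-off are given. Protocol 3.1 (CO from everyone) and 7.10 (CO compared with self-report) favour agreement among all submitters. Protocol 8.3 speaks more loosely of confirmation, so the denominator remains unstated.
- **First illustration.** It assumes that every self-reported smoker reads high. The split survives only if at most 13 of the 110 read low (117/137 = 85.4%); at 14, both definitions fail (116/137 = 84.7%). The second illustration is unaffected.
- **Imputation.** A reader might infer that the ITT rule inflates concordance. The rule imputes a smoking status, not a ppm value, and Protocol 1.3 describes the convention in terms of an unreturned survey. The Data Analysis Plan neither includes nor excludes CO. Under the broad reading, a claimed abstainer without a CO reading would also become discordant, which pulls the other way.
- **Recent quitters.** A reader might infer that people who last smoked 8-30 days ago, who report smoking but may read low, push agreement below 85%. The documents' figures do not show this. The pilot completer gap is 51.5 − 29.9 = 21.6 points. A proportional QuitGuide gap is 21.6 × (8.3/87.7)/29.9 = 6.8 points. Even if all of them read low, pooled agreement is 100 − (21.6 + 6.8)/2 = 85.8%.
- **Status of the 8 ppm text.** The monitoring plan also differs from the Protocol on the Android version and on a pre-screening call, so it may be leftover earlier text. That is inference; no precedence is stated.

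**Conclusion.** The concern holds for a secondary feasibility objective and should be fixed. Protocol 2.2 draws a conclusion that its comparison cannot support. With 50 against 87, and assumed concordance of 75-95%, power for a 10-point difference is 28-52% and a null result excludes only large differences. These figures assume pilot retention and CO from every completer. Self-selection means that even a precise comparison would not isolate the effect of monitoring.

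The cut-off conflict is literal and its effect cannot be sized. The missing denominator can reverse the verdict on the 85% benchmark. The imputation effect is conditional on one reading and narrow (three counts out of 137).

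A reader might infer that the primary result is at risk. The self-report primary test in Protocol 10.3 and SAP 10.3 uses neither CO nor concordance and is not affected. The CO-confirmed wording of the primary outcome in Protocol 3.1 is a separate matter to reconcile.

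**What to change.** Before database lock:

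1. **Video comparison.** In Protocol 2.2, delete the inference that non-significance demonstrates validity. In Protocol 10.4, SAP 10.4 and the Data Analysis Plan, state that the video versus non-video difference is reported with a 95% CI, that comparability is claimed only if the interval lies within a pre-stated margin, and that the video group is self-selected.
2. **Cut-off.** Reconcile the 7 ppm passages (Protocol 3.1, 8.3, 11.1) with the 8 ppm passage (monitoring plan, Data Acquisition).
3. **Benchmark.** Compute concordance in participants with both a survey answer and a CO reading, without imputation, as a stated exception to the all-analyses ITT rule. Report both overall agreement and CO confirmation among self-reported 30-day abstainers, each with an exact 95% CI. Name the one to which the 85% applies. Report missing CO by arm and by self-reported status.

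**Cost.** Wording only, no new data. The confirmation rate will be imprecise: 23/27, the lowest passing count, has an exact 95% CI of 66-96%. The video comparison will probably be inconclusive near 10 points, since the half-width alone is 10.4 points at 90% concordance. Restricting to people with both measures departs from ITT. The health-plan partner must confirm which definition its 85% refers to.
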